4.4 Heterogeneity of Treatment Effects Analysis for APHAB scores

Compare APHAB change scores between the two arms at the end of month 3 vs baseline while adjusting for interaction terms between treatment and each variable of interest.

Analysis: This will be done for all randomized patients who have both baseline and 3 month scores (“completers”). The primary analysis will be performed by linear regression and include randomized assignment, clinical site, a given variable of interest (denoted by S), and interactions between treatment and the variable of interest, with separate models fit for each variable of interest. The two variables of interest that decided to investigate are income group (simplified version – below median, above median, prefer not to answer) and hearing loss classification (mild, moderate). Interactions will be tested at the 0.15 level. If the overall test for the interaction is significant, forest plots will be constructed to examine the heterogeneity of treatment effect and formal treatment by factor interaction terms tested in the models. The general model structure is:

$$APHAB \text{ change score} = \beta_0 + \beta_1 * \text{treatment} + \beta_2 * \text{site} + \beta_S * S + \beta_{ST} * S * \text{treatment}$$

Table 4: Linear Regression Beta Estimates for Variable S Model
Outcome Modelled: APHAB Change Score

Covariate	Beta	95% C.I.	P-Value*
Hearing Aid Assignment (Reference: Bilateral)			
Unilateral	XXX	(XXX , XXX)	XXX
Clinical Site (Reference: Duke)			
Vanderbilt	XXX	(XXX , XXX)	XXX
Variable S	XXX	(XXX, XXX)	XXX
HA Assignment*Variable S	XXX	(XXX, XXX)	XXX

4.5 Sensitivity analyses for APHAB scores

If more than 5% of randomized patients have missing APHAB scores at 3 months, we will use multiple imputation in an intent to treat sensitivity analysis.

Analysis 1: An imputation model via linear regression will be developed based on available data and will include initial APHAB scores, treatment, baseline characteristics, and possible interactions of these variables with treatment. The specific variables of interest to include are: treatment, site, income group, and baseline APHAB. A total of 1000 datasets with imputations of APHAB score reduction will be generated using this model. Each dataset will be analyzed using linear regression models as described in section 4.3. The combined results will be reported and will take the variability of multiple imputations into account.

Analysis 2: The characteristics from the participants with completed data will be compared to those with missing APHAB data with the use of a “Table 1”. We may also include treatment randomization in this table.

Table 5: Patient Characteristics for Missing and Non-Missing APHAB

	Missing APHAB (N=XXX)	Not Missing APHAB (N=XXX)	Total (N=XXX)
Assignment			
Unilateral	XXX (%)	XXX (%)	XXX (%)
Bilateral	XXX (%)	XXX (%)	XXX (%)
Clinical Site			
Duke	XXX (%)	XXX (%)	XXX (%)
Vanderbilt	XXX (%)	XXX (%)	XXX (%)
Gender			
Female	XXX (%)	XXX (%)	XXX (%)
Male	XXX (%)	XXX (%)	XXX (%)
Other	XXX (%)	XXX (%)	XXX (%)
Age at Baseline Visit			
N	XXX	XXX	XXX
Missing	XXX	XXX	XXX
Mean (SD)	XXX (XXX)	XXX (XXX)	XXX (XXX)
Median	XXX	XXX	XXX
Q1, Q3	XXX , XXX	XXX , XXX	XXX , XXX
Range	XXX - XXX	XXX - XXX	XXX - XXX
Race			
American Indian/Alaska Native	XXX (%)	XXX (%)	XXX (%)
Asian	XXX (%)	XXX (%)	XXX (%)
Black or African American	XXX (%)	XXX (%)	XXX (%)
White	XXX (%)	XXX (%)	XXX (%)
More than one race	XXX (%)	XXX (%)	XXX (%)
Native Hawaiian/Pacific Islander	XXX (%)	XXX (%)	XXX (%)
Declined	XXX (%)	XXX (%)	XXX (%)
Ethnicity			

Hispanic or Latino	XXX (%)	XXX (%)	XXX (%)
Not Hispanic or Latino	XXX (%)	XXX (%)	XXX (%)
Declined	XXX (%)	XXX (%)	XXX (%)
Personal Income Last Year			
\$0	XXX (%)	XXX (%)	XXX (%)
\$1 to \$9999	XXX (%)	XXX (%)	XXX (%)
\$10,000 to \$24,999	XXX (%)	XXX (%)	XXX (%)
\$25,000 to \$49,999	XXX (%)	XXX (%)	XXX (%)
\$50,000 to \$74,999	XXX (%)	XXX (%)	XXX (%)
\$75,000 to \$99,999	XXX (%)	XXX (%)	XXX (%)
\$100,000 to \$149,999	XXX (%)	XXX (%)	XXX (%)
\$150,000 or greater	XXX (%)	XXX (%)	XXX (%)
Prefer not to answer	XXX (%)	XXX (%)	XXX (%)
Personal Income Last Year (Categorical)			
Below Median	XXX (%)	XXX (%)	XXX (%)
Above Median	XXX (%)	XXX (%)	XXX (%)
Prefer not to answer	XXX (%)	XXX (%)	XXX (%)
Hearing Aid Health Insurance Benefits			
No	XXX (%)	XXX (%)	XXX (%)
Yes	XXX (%)	XXX (%)	XXX (%)
Not sure	XXX (%)	XXX (%)	XXX (%)
Marital Status			
Married	XXX (%)	XXX (%)	XXX (%)
Widowed	XXX (%)	XXX (%)	XXX (%)
Divorced	XXX (%)	XXX (%)	XXX (%)
Separated	XXX (%)	XXX (%)	XXX (%)
Never married	XXX (%)	XXX (%)	XXX (%)
Prefer not to answer	XXX (%)	XXX (%)	XXX (%)
Living Arrangements			
Alone	XXX (%)	XXX (%)	XXX (%)
With spouse	XXX (%)	XXX (%)	XXX (%)
With spouse and others	XXX (%)	XXX (%)	XXX (%)
Other	XXX (%)	XXX (%)	XXX (%)
Prefer not to answer	XXX (%)	XXX (%)	XXX (%)
Education			
Less than high school	XXX (%)	XXX (%)	XXX (%)
High school	XXX (%)	XXX (%)	XXX (%)
Some college	XXX (%)	XXX (%)	XXX (%)
4-year degree	XXX (%)	XXX (%)	XXX (%)
Graduate degree	XXX (%)	XXX (%)	XXX (%)
Other	XXX (%)	XXX (%)	XXX (%)
Quarter of Baseline Visit			
2021 Q2	XXX (%)	XXX (%)	XXX (%)

2021 Q3	XXX (%)	XXX (%)	XXX (%)
...	XXX (%)	XXX (%)	XXX (%)
Total MoCA Score			
N	XXX	XXX	XXX
Missing	XXX	XXX	XXX
Mean (SD)	XXX (XXX)	XXX (XXX)	XXX (XXX)
Median	XXX	XXX	XXX
Q1, Q3	XXX , XXX	XXX , XXX	XXX , XXX
Range	XXX - XXX	XXX - XXX	XXX - XXX
Pure Tone Average in Better Ear			
N	XXX	XXX	XXX
Missing	XXX	XXX	XXX
Mean (SD)	XXX (XXX)	XXX (XXX)	XXX (XXX)
Median	XXX	XXX	XXX
Q1, Q3	XXX , XXX	XXX , XXX	XXX , XXX
Range	XXX - XXX	XXX - XXX	XXX - XXX
Hearing Loss Classification			
Mild	XXX (%)	XXX (%)	XXX (%)
Moderate	XXX (%)	XXX (%)	XXX (%)

(report generated on XXXXXXX)

Analysis 3: We will report the rate of dropout in each of the two groups and look at the potential imbalances in dropouts between randomized interventions. We will report clinically meaningful differences. Given the size of the study, the ability to detect MNAR is small.

4.6 Analyze APHAB binary response at 3 months

Patients with a decrease of at least 25 units on the APHAB scale at month 3 compared to baseline unaided APHAB will be defined as “responders.” Patients who do not meet this criterion of 25 units, do not return, or do not have a score at month 3 will be defined as “non-responders.” If there are any patients with unaided APHAB scores of less than 25, these patients will be excluded as they are not eligible to drop 25 units.

Analysis 1: This will be done for all randomized patients who are eligible, including those missing APHAB change scores. This analysis will be performed by logistic regression and include randomized assignment and clinical site as covariates.

$$\text{Binary APHAB change score} = \beta_0 + \beta_1 * \text{treatment} + \beta_2 * \text{site}$$

Table 6: Logistic Regression OR Estimates

Outcome Modelled: Binary APHAB Change Score Response (25 Unit)

Covariate	OR	95% C.I.	P-Value*
Hearing Aid Assignment (Reference: Bilateral)			
Unilateral	XXX	(XXX , XXX)	XXX
Clinical Site (Reference: Duke)			
Vanderbilt	XXX	(XXX , XXX)	XXX

*Using XXX statistic

Analysis 2 (heterogeneity of treatment effects): This analysis will be performed by logistic regression and include randomized assignment, clinical site, a given variable of interest (denoted by S), and interactions between treatment and the variable of interest, with separate models fit for each variable of interest. The two variables of interest that decided to investigate are income group (simplified version – below median, above median, prefer not to answer) and hearing loss classification (mild, moderate). Interactions will be tested at the 0.15 level. If the overall test for the interaction is significant, forest plots will be constructed to examine the heterogeneity of treatment effect and formal treatment by factor interaction terms tested in the models. The general model structure is:

$$\text{Binary APHAB change score} = \beta_0 + \beta_1 * \text{treatment} + \beta_2 * \text{site} + \beta_S * S + \beta_{ST} * S * \text{treatment}$$

We will report the joint test p-value for the interaction term. If significant, we will report odds ratios and 95% confidence intervals.

Table 7 Logistic Regression OR Estimates for Variable S Model
Outcome Modelled: Binary APHAB Change Score Response (25 Unit)

Covariate	OR	95% C.I.	P-Value*
Hearing Aid Assignment (Reference: Bilateral)	XXX	(XXX , XXX)	XXX
Unilateral	XXX	(XXX , XXX)	XXX
Clinical Site (Reference: Duke)	XXX	(XXX, XXX)	XXX
Vanderbilt	XXX	(XXX, XXX)	XXX
Variable S	XXX	(XXX, XXX)	XXX
HA Assignment*Variable S	XXX	(XXX, XXX)	XXX

*Using XXX statistic

Analyses 3-4: repeat analyses 1-2 of this section, but define responders as having a decrease of at least 15 units.

$$\text{Binary APHAB change score} = \beta_0 + \beta_1 * \text{treatment} + \beta_2 * \text{site}$$

Table 8 Logistic Regression OR Estimates
Outcome Modelled: Binary APHAB Change Score (15 Unit)

Covariate	OR	95% C.I.	P-Value*
Hearing Aid Assignment (Reference: Bilateral)	XXX	(XXX , XXX)	XXX
Unilateral	XXX	(XXX , XXX)	XXX
Clinical Site (Reference: Duke)	XXX	(XXX , XXX)	XXX
Vanderbilt	XXX	(XXX , XXX)	XXX

*Using XXX statistic

$$\text{Binary APHAB change score} = \beta_0 + \beta_1 * \text{treatment} + \beta_2 * \text{site} + \beta_S * S + \beta_{ST} * S * \text{treatment}$$

Table 9 Logistic Regression OR Estimates for Variable S Model
Outcome Modelled: Binary APHAB Change Score (15 Unit)

Covariate	Beta	95% C.I.	P-Value*
-----------	------	----------	----------

Hearing Aid Assignment (Reference: Bilateral)			
Unilateral	XXX	(XXX , XXX)	XXX
Clinical Site (Reference: Duke)			
Vanderbilt	XXX	(XXX , XXX)	XXX
Variable S	XXX	(XXX, XXX)	XXX
HA Assignment*Variable S	XXX	(XXX, XXX)	XXX

*Using XXX statistic

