3.1 Primary Outcome(s)

Outcome	Description	Variables and Source	Specifications
APHAB Change Score	Difference in aided APHAB scores at month 3 and unaided scores at baseline	aphab_change	Scale score – will need to calculate global communication scores at baseline (unaided) and 3 months (aided), subtract (3 months – baseline) A lower score on APHAB is better.

			
Rescore variables and multiply by 100
 
 • 1 = 0.99 • 2 = 0.87 • 3 = 0.75 • 4 = 0.50 • 5 = 0.25 • 6 = 0.12 • 7 = 0.01 
Reverse score questions 1, 9, 11, 16, 19, 21
 
Global score: mean of variables in the EC, BN, RV subscale scores (excludes questions 3, 8, 13, 17, 20, 22)
 
Note: APHAB has 4 subscales and a global communication scale. The study is powered based on the benefit score on the global communication scale (August 2019 draft – APHAB SD of 25 with different levels of Cohen's D).

--	--	--	--

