3.2 Secondary Outcome(s)

Outcome	Description	Variables and Source	Specifications
APHAB change score – binary, 3 months	Responders vs non-responders for primary APHAB outcome	
Decrease of 25 units: use aphab_change_responder
 
Decrease of 15 units: use aphab_change_responder _15
	
Patients with a decrease of at least 25 units (or 15 units for the sensitivity analysis) on the APHAB scale at month 3 will be considered “responders.” Patients not returning or who do not have a score at 3 months will be considered “non-responders.” Patients with a baseline score < 25 (or < 15) are ineligible (missing).
 
Binary (25 unit decrease):
 
 • Missing if baseline score <25 • 1 if aphab_change <=-25

			
 • 0 else 
Binary (15 unit decrease);
 
 • Missing if baseline score <15 • 1 if aphab_change <=-15 • 0 else
APHAB – 4 subscales	EC, BN, RV, AV scales at both baseline and 3 months, as well as change scores	
Baseline variables:
 
aphab_ec_base aphab_bn_base aphab_rv_base aphab_av_base
 
3-month variables:
 
aphab_ec_3m aphab_bn_3m aphab_rv_3m aphab_av_3m
 
Change scores:
 
aphab_ec_change aphab_bn_change aphab_rv_change aphab_av_change
	
Rescore variables and multiply by 100
 
 • 1 = 0.99 • 2 = 0.87 • 3 = 0.75 • 4 = 0.50 • 5 = 0.25 • 6 = 0.12 • 7 = 0.01 
Reverse score questions 1, 9, 11, 16, 19, 21
 
EC: mean of questions 4, 10, 12, 14, 15, 23
 
BN: mean of questions 1, 6, 7, 16, 19, 24
 
RV: mean of questions 2, 5, 9, 11, 18, 21
 
AV: mean of questions 3, 8, 13, 17, 20, 22

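### The responder cut-offs (baseline below 25 or 15) assume the lowest APHAB global score is 0, but the SAP's scoring makes it 1, so any patient with a baseline of 25 to <26 (or 15 to <16) would be a non-responder by construction

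*SAP*

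**What the plan says.** Section 3.1 of the primary-analysis SAP maps the seven response codes to 0.99, 0.87, 0.75, 0.50, 0.25, 0.12 and 0.01, with the instruction "Rescore variables and multiply by 100". The total is defined as "Global score: mean of variables in the EC, BN, RV subscale scores", which leaves 18 of the 24 items.

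Section 3.2 builds two responder variables from the change in that score (3 months minus baseline). For the 25-unit version the coding is "Missing if baseline score <25", then "1 if aphab_change <=-25", and 0 for everyone else. The 15-unit version has the same structure, with "Missing if baseline score <15".

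Section 4.6 gives the reason for the exclusion: "these patients will be excluded as they are not eligible to drop 25 units". Table 2 of the same SAP reports the excluded patients in rows for those ineligible to drop 25 or 15 units and omits them from the percentages. Section 3.1 of the 6-month SAP repeats both limits, and its Table 1 has the same rows.

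**The concern.** The exclusion is meant to remove patients for whom the required drop is impossible. A cut-off equal to the drop does that only if the score can reach 0. If the floor is higher, a strip of patients just above the cut-off meets the SAP's reason for exclusion but is kept and coded as failing. Such patients lower the responder rate in both arms, and the row of ineligible patients could be slightly incomplete. This would affect the 25-unit and 15-unit responder analyses at 3 and 6 months.

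**Working it through.** **Inputs.** The item values, global score, limits and responder rule are those set out above. Planned enrolment is 350 (protocol, section 6). The documents do not give the baseline mean or SD. The SD of 25 in SAP section 3.1 belongs to the power basis and is not described as a baseline SD. I therefore assume a mean of 40 to 60 and an SD of 12 to 25.

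**Step 1: the plan's own figure.** Smallest baseline that permits the drop = required drop + lowest possible score. The limits of 25 and 15 come out as 25 + 0 and 15 + 0, so they need a floor of 0.

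**Step 2: the floor under the SAP's scoring.** After multiplication by 100 an item takes one of the values 99, 87, 75, 50, 25, 12 or 1. Six items are reversed ("Reverse score questions 1, 9, 11, 16, 19, 21"). Reversing by response code gives the same seven values; reversing as 100 minus the value gives 1, 13, 25, 50, 75, 88 and 99. The minimum is 1 either way. A mean of values that are each at least 1 is at least 1, so the global score runs from 18/18 = 1 to (18 × 99)/18 = 99.

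**Step 3: limits that fit the stated reason.** 25 + 1 = 26 and 15 + 1 = 16.

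**Step 4: who is caught.** The score is a whole-number sum divided by 18.
- 25-unit rule: sums of 450 to 467 give baselines of 25.00 to 25.94 (18 attainable values). The largest possible drops are 24.00 to 24.94, so a change of −25 cannot occur.
- 15-unit rule: sums of 270 to 287 give baselines of 15.00 to 15.94 (18 attainable values). The largest possible drops are 14.00 to 14.94.

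**Step 5: how many patients.** For a normal baseline with mean m and SD s, truncated to 1–99, the expected number in the band from L to L + 1 is 350 × [Φ((L+1−m)/s) − Φ((L−m)/s)] / [Φ((99−m)/s) − Φ((1−m)/s)]. Percentages are of the patients who remain after the exclusion.

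| Assumed mean, SD | Patients in 25 to <26 | Patients in 15 to <16 |
|---|---|---|
| 40, 15 | 5.86 (1.98%) | 2.46 (0.74%) |
| 40, 25 | 5.07 (1.88%) | 3.71 (1.19%) |
| 50, 20 | 3.34 (1.06%) | 1.60 (0.47%) |
| 55, 20 | 2.39 (0.73%) | 1.01 (0.29%) |
| 60, 12 | 0.19 (0.05%) | 0.01 (0.00%) |

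Over the grid examined (means 40 to 60 in steps of 5; SDs 12, 15, 20 and 25), the extremes are 0.19 and 5.86 patients for the 25-unit rule, and 0.01 and 3.71 for the 15-unit rule.

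**Step 6: effect on the comparison.** Suppose a share f of the included patients in each arm cannot respond. Each true rate p becomes p(1 − f). Take illustrative rates of 50% and 65%, where the odds ratio is (0.65/0.35)/(0.50/0.50) = 1.857, and assume 170 patients per arm.
- f = 1%: the rates become 49.5% and 64.35%; the odds ratio is (0.6435/0.3565)/(0.495/0.505) = 1.842. Power goes from 79.8% to 79.2%, about 0.5 points before rounding.
- f = 2%: the rates become 49.0% and 63.7%; the odds ratio is 1.826. Power goes from 79.4% to 78.3%, about 1.1 points.

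The first power figure in each pair is for the analysis with those patients removed.

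**The case against.** The best defence is that nothing of consequence follows. The responder outcome is secondary. The limit rests on a pre-treatment score and applies identically to both arms, so no imbalance between randomised arms is built in. Moving it by one unit also changes little in substance: at a baseline of exactly 26, response needs all 18 items at their lowest value at month 3, so patients just above the new limit are near-certain non-responders too. Softening the stated reason would reconcile the text as well as changing the number. All of this stands and limits the point to a minor one. It does not rescue the cut-off, because the SAP presents it as the point below which the drop is impossible and not as a convention.

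Three stronger readings are tempting and are not supported:
- *That patients have been misclassified.* The tables are empty shells and no baseline distribution is given, so the band may contain nobody.
- *That the row of ineligible patients is mislabelled.* Everyone with a baseline below 25 truly cannot drop 25 units. The row can only be incomplete.
- *That the treatment comparison is materially biased.* By design the rule does not differ between arms, and the illustrated shift in the odds ratio is in the second decimal place.

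**Conclusion.** Wrong as written, minor. That the limits should be 26 and 16 follows from the SAP's scoring alone and needs no assumption. The size does rest on assumptions: with a truncated normal baseline, mean 40 to 60, SD 12 to 25 and 350 patients, about 0 to 6 patients fall in the 25-unit band and about 0 to 4 in the 15-unit band, at most about 2.0% and 1.2% of those included. Responder rates move slightly down and the odds ratio slightly toward 1. The same holds for the 6-month responder percentages, which that SAP compares by chi-square test. The primary analysis of the continuous change score (section 4.3) does not use the cut-offs and is unaffected.

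**What to change.** Set the ineligible limits to baseline <26 for the 25-unit outcome and <16 for the 15-unit outcome (required drop + 1) in sections 3.2 and 4.6 of the primary-analysis SAP, in section 3.1 of the 6-month SAP, and in the code. The lesser alternative is to keep 25 and 15 and no longer describe them as the point where the drop becomes impossible.

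The data were locked on 10/17/2024, so record the change in a dated SAP note that states how many patients it moves in each arm. If none move, the note can say so and the results stand.

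The cost is two numbers per SAP and a small post-lock change to the denominator of a secondary outcome. No data collection changes.

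A separate matter for the same edit: section 3.2 of the hearing aid choice and switching SAP defines the same responder variables with no baseline exclusion at all, and should be aligned.

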4.7 Describe APHAB Subscales

We will describe the distribution of the 4 APHAB subscales (EC, BN, RV, AV) at baseline (unaided) and 3 months (aided) by hearing aid assignment, along with the change scores graphically and in a Table (Table 10).

Table 10: APHAB Subscale Distributions

	Unilateral (N=XXX)	Bilateral (N=XXX)	Total (N=XXX)
APHAB EC Subscale (Baseline)			
N	XXX	XXX	XXX
Missing	XXX	XXX	XXX
Mean (SD)	XXX (XXX)	XXX (XXX)	XXX (XXX)
Median	XXX	XXX	XXX
Q1, Q3	XXX , XXX	XXX , XXX	XXX , XXX
Range	XXX - XXX	XXX - XXX	XXX - XXX
APHAB EC Subscale (3 Months)			
N	XXX	XXX	XXX
Missing	XXX	XXX	XXX
Mean (SD)	XXX (XXX)	XXX (XXX)	XXX (XXX)
Median	XXX	XXX	XXX
Q1, Q3	XXX , XXX	XXX , XXX	XXX , XXX
Range	XXX - XXX	XXX - XXX	XXX - XXX
APHAB EC Subscale Change Score			
N	XXX	XXX	XXX
Missing	XXX	XXX	XXX
Mean (SD)	XXX (XXX)	XXX (XXX)	XXX (XXX)
Median	XXX	XXX	XXX
Q1, Q3	XXX , XXX	XXX , XXX	XXX , XXX
Range	XXX - XXX	XXX - XXX	XXX - XXX
APHAB BN Subscale (Baseline)			
N	XXX	XXX	XXX
Missing	XXX	XXX	XXX
Mean (SD)	XXX (XXX)	XXX (XXX)	XXX (XXX)
Median	XXX	XXX	XXX
Q1, Q3	XXX , XXX	XXX , XXX	XXX , XXX
Range	XXX - XXX	XXX - XXX	XXX - XXX

APHAB BN Subscale (3 Months)

N	XXX	XXX	XXX
Missing	XXX	XXX	XXX
Mean (SD)	XXX (XXX)	XXX (XXX)	XXX (XXX)
Median	XXX	XXX	XXX
Q1, Q3	XXX , XXX	XXX , XXX	XXX , XXX
Range	XXX - XXX	XXX - XXX	XXX - XXX

APHAB BN Subscale Change Score

N	XXX	XXX	XXX
Missing	XXX	XXX	XXX
Mean (SD)	XXX (XXX)	XXX (XXX)	XXX (XXX)
Median	XXX	XXX	XXX
Q1, Q3	XXX , XXX	XXX , XXX	XXX , XXX
Range	XXX - XXX	XXX - XXX	XXX - XXX

APHAB RV Subscale (Baseline)

N	XXX	XXX	XXX
Missing	XXX	XXX	XXX
Mean (SD)	XXX (XXX)	XXX (XXX)	XXX (XXX)
Median	XXX	XXX	XXX
Q1, Q3	XXX , XXX	XXX , XXX	XXX , XXX
Range	XXX - XXX	XXX - XXX	XXX - XXX

APHAB RV Subscale (3 Months)

N	XXX	XXX	XXX
Missing	XXX	XXX	XXX
Mean (SD)	XXX (XXX)	XXX (XXX)	XXX (XXX)
Median	XXX	XXX	XXX
Q1, Q3	XXX , XXX	XXX , XXX	XXX , XXX
Range	XXX - XXX	XXX - XXX	XXX - XXX

APHAB RV Subscale Change Score

N	XXX	XXX	XXX
Missing	XXX	XXX	XXX
Mean (SD)	XXX (XXX)	XXX (XXX)	XXX (XXX)
Median	XXX	XXX	XXX
Q1, Q3	XXX , XXX	XXX , XXX	XXX , XXX
Range	XXX - XXX	XXX - XXX	XXX - XXX

APHAB AV Subscale (Baseline)

N	XXX	XXX	XXX
Missing	XXX	XXX	XXX
Mean (SD)	XXX (XXX)	XXX (XXX)	XXX (XXX)
Median	XXX	XXX	XXX
Q1, Q3	XXX , XXX	XXX , XXX	XXX , XXX
Range	XXX - XXX	XXX - XXX	XXX - XXX

APHAB AV Subscale (3 Months)

N	XXX	XXX	XXX
---	-----	-----	-----

Missing	XXX	XXX	XXX
Mean (SD)	XXX (XXX)	XXX (XXX)	XXX (XXX)
Median	XXX	XXX	XXX
Q1, Q3	XXX , XXX	XXX , XXX	XXX , XXX
Range	XXX - XXX	XXX - XXX	XXX - XXX

APHAB AV Subscale Change Score

N	XXX	XXX	XXX
Missing	XXX	XXX	XXX
Mean (SD)	XXX (XXX)	XXX (XXX)	XXX (XXX)
Median	XXX	XXX	XXX
Q1, Q3	XXX , XXX	XXX , XXX	XXX , XXX
Range	XXX - XXX	XXX - XXX	XXX - XXX

(report generated on XXXXXXX)

4.8 Initially planned analyses that we will not do

We had initially planned to conduct adjusted analyses for the outcomes of global change score and both responder definitions. After reviewing cell counts of demographics at baseline and discussion, we decided that there are no variables of interest to include in an adjusted model.

Statistical Analysis Plan (SAP) – Secondary (3-Month) Outcomes and Descriptives

Project: Evaluation of Unilateral vs Bilateral Hearing Aids for the Treatment of Age-related Hearing Loss

IRB Number: Pro00106077

Investigator(s): [name], AuD, PhD

Biostatistician(s): [name], [name], [name]

Original Creation Date: 12.15.2021

Version Date: 09.30.2024

Investigator Agreement

- All statistical analyses included in an abstract or manuscript should reflect the work of the biostatistician(s) listed on this SAP. No changes or additional analyses should be made to the results or findings without discussing with the project biostatistician(s).
- All biostatisticians on this SAP should be given sufficient time to review the full presentation, abstract, manuscript, or grant and be included as co-authors on any abstract or manuscript resulting from the analyses.
- If substantial additional analysis is necessary or the aims of the project change, a new SAP will need to be developed.
- Publications resulting from this SAP are supported in part by the Duke CTSA and must cite grant number UL1TR002553 and be submitted to PubMed Central.
- I have reviewed the SAP and understand that any changes must be documented.

Acknowledged by: Click or tap here to enter text.

Date: Click or tap to enter a date.

Activity Log

- 11.16.2023 Split secondary outcomes SAP into multiple SAPs
- 05.31.2024 Added additional variables
- 07.11.2024 Resolved some questions about variables (see SAP dated 20240531 and Overview of All Planned Analysis dated 20240620)
- 07.25.2024 Moved GHABP from the GHABP/EMA SAP to this SAP
- 09.30.2024 Updated variable names, resolved comments from previous SAP dated 20240725)

Acronyms

APHAB	Abbreviated Profile of Hearing Aid Benefit
EMA	Ecological Momentary Assessment
GHABP	Glasgow Hearing Aid Benefit Profile
IOI-HA	International Outcomes Inventory for Hearing Aids
SADL	Satisfaction with Amplification in Daily Life
SSQ	Speech Spatial Qualities
HHIE	Hearing Handicap Inventory for Elderly

1 Study Overview

Background/Introduction: The overall goal of the project is to determine the benefit of unilateral or bilateral hearing aid fittings in adults with mild-to-moderate age-related hearing loss. This will address the lack of high-quality evidence supporting bilateral hearing aids over unilateral hearing aids. This project will use a randomized controlled trial with two treatment arms: a bilateral hearing aid fitting group and a unilateral hearing aid fitting group.

